#### Behavioural neurocognitive testing (excluding FERT)

Comparison of ANCOVA or linear mixed models to compare groups (prucalopride versus placebo) over two time points (baseline versus follow up).

#### **FERT**

As in previous work [21, 22], FERT data will be analysed using repeated measures analyses of variance (ANOVAs). Group (prucalopride or placebo) will be the between-subject factor, and emotion (6 levels) will be the within-subject factor.

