#### Study Visit 2 (baseline and randomisation) & Study Visit 3 (Follow-up after 7-10 days medication):

All procedures are the same for visit 2 and 3 unless otherwise specified

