#### 1) Questionnaires:

- -7-item Psychotic Like Experiences (PLE) questionnaire [17]
- -Perceived Deficits Questionnaire (PDQ) subjective cognition scale
- -Patient Health Questionnaire (PHQ-9) depression scale

UNIVERSITYOF BIRMINGHAM

-Generalised Anxiety Disorder Assessment (GAD-7) anxiety scale

- -Snaith-Hamilton Pleasure Scale (SHAPS) anhedonia scale
- -Side effects checklist
- 2) Neurocognitive battery suitable for repeated measures known to be sensitive to 5-HT4 agonism in previous studies
- -Auditory Verbal Learning Task (AVLT)
- -Working memory (N-back)
- -Facial Expression Recognition Task (FERT)
- -Probabilistic Instrumental Learning Task (PILT)
- 3) MRI / MRS scan (as in (17)) including physiological assessment (heart rate variability)
- -Structural (T1) (Baseline visit only)
- -Resting state fMRI scan
- -Magnetic Resonance Spectroscopy (MRS)
- 5) **Blood samples** (pre- and on-drug/placebo samples): for preparation/storage and analysis of immune cell phenotypes/biomarkers and prucalopride levels
- A blood sample of approximately 20ml (1.25 tablespoons) will be collected to measure: IL-1b, IL-6, IL-10, TNFa, IFNg, BDNF, S100B and SuPAR and prucalopride levels
- Blood samples will be collected by a qualified phlebotomist / trained clinician at two separate study time points (baseline and after 7-10 days' of medication).
- The intention behind taking the blood samples is to process them for the purpose of analysis of subcellular components (all biomarkers and drug levels will be analysed from plasma / serum).
- After collection, blood samples will be transported to [name] Laboratory group based in the College of Medical and Dental Sciences, Institute for Clinical Sciences at the University of Birmingham on the same day for preprocessing and storage as per their Standard Operating Procedures. This will include the use of the HBRC for storage of cellular material for analysis in future studies. Pre-processing to cellular / acellular components and transfer of cellular material to the HBRC will occur within one week of collection. After pre-processing, plasma and serum will be stored in [name]' Laboratory until required for analysis.
- 6) Optional Microbiome analysis (collection to take place at home):

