#### 8.3.5 Neurocognitive tests (40 minutes) – BASELINE AND FOLLOW-UP

We will undertake three different neurocognitive tasks that have previously been sensitive to change with 5-HT4R agonism – an auditory verbal learning task (AVLT), a working memory task (N-back), a facial expression recognition task (FERT), and a reward learning task (PILT). These will be delivered using electronic equipment where necessary. For the AVLT, participants are read a list of 15 words 5 times, after each reading they are asked to recall as many of the words as necessary. They are then asked to recall these words again after a short (3 minutes) delay – where they are read a different list of 15 words – and long (20-30 minutes) delay. For the N-back, participants are asked to recall the letter / number shown in a sequence either just before the current letter / number, or 1 before (1-back), 2 before (2-back), or 3 before (3-back). During the FERT, participants are shown a face on a computer screen briefly (circa 0.5s) and then asked to identify the emotion shown from happy / sad / fear / anger / disgust / surprise / neutral. Facial expressions are graded in terms of proximity to neutral (from 10% to 100%). In the PILT, for each trial, the participant is presented with 2 stimuli that have reciprocal probabilities (0.7 vs. 0.3) of a win outcome (plus 20 points) versus a no-win outcome (0 points) in reward condition trials or a loss outcome (minus 20 points) versus a no-loss outcome (0 points) in loss-

UOB ethics number: ERN 3117

condition trials. Participants chose one of the two stimuli, following which they received visual feedback on the trial outcome and their current total earnings. Each block of the PILT consists of 30 reward trials and 30 loss trials. Participants performed 3 blocks of the PILT in each behavioural testing session. Different task stimuli are used in each block. The behavioural measure of interest is choice accuracy.

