#### 8.5 Outcomes

Primary: The effect of 7-10 days' prucalopride versus placebo on neurocognitive task performance.

Secondary include: Prucalopride's effects on subjective cognition, other measures (including mood/anxiety symptoms), task and resting state functional connectivity (cognitive versus affective networks). Blood samples will allow subsequent association of responders with biomarkers and drug levels.

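### The FERT model is fixed as group and emotion only, so the pre-drug FERT score has no stated role and precision is lost on a task in the primary battery

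*Protocol*

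**What the plan says.** - **Collection.** Section 8.1 lists FERT among four tasks in the neurocognitive battery for Visits 2 and 3 and says "All procedures are the same for visit 2 and 3 unless otherwise specified". The heading of section 8.3.5 is "Neurocognitive tests (40 minutes) – BASELINE AND FOLLOW-UP", and the schedule of assessments ticks cognitive testing at both visits. Randomisation and the handing out of medication take place at Visit 2, so the Visit 2 score is a pre-drug measurement.
- **Status.** Section 8.5 reads "Primary: The effect of 7-10 days' prucalopride versus placebo on neurocognitive task performance". No task is singled out or excluded.
- **Model for the other tasks.** Section 17.1 plans "Comparison of ANCOVA or linear mixed models to compare groups (prucalopride versus placebo) over two time points (baseline versus follow up". The heading of that paragraph excludes FERT.
- **Model for FERT.** The next paragraph specifies a repeated measures ANOVA, modelled on earlier published work: "Group (prucalopride or placebo) will be the between-subject factor, and emotion (6 levels) will be the within-subject factor". It does not say which visit or which score enters, and it names neither a time factor nor a baseline covariate.
- **Covariates elsewhere.** Risk 3 in section 12 recognises that sub-clinical cognitive and mood differences at entry may hide a signal. It allows optional adjustment for baseline mood and subjective cognition, but does not mention baseline FERT.

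**The concern.** The questionnaires and the other three tasks are all given models that refer to two time points. FERT is the only behavioural or questionnaire measure that is not, and the heading shows that the separation is deliberate. An analysis plan that follows the FERT paragraph literally on Visit 3 data would collect a pre-drug score from every participant and never use it.

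Precision is at stake, not bias. With at most 18 participants per group, between-person variation in face recognition makes up much of the noise in the group comparison. The Visit 2 score is the obvious variable to remove part of it. How much it removes depends on how strongly the two visits correlate.

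**Working it through.** **Inputs from the Protocol (section 16.1).** Effect size 0.5-0.7, read here as a standardised mean difference d because the metric is not stated; 15-17 analysable per group; 0.05 false positive rate, taken as two-sided. The calculations use n = 17, the upper end of that range.

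**Assumed input.** The correlation r between Visit 2 and Visit 3 FERT scores is not given. The range 0.3 to 0.8 is shown.

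**The Protocol's own power figure.** Section 16.1 states 85-90% power with 15-17 per group. A two-sided, two-group test on follow-up scores does not reproduce this: it gives 26-29% at d = 0.5 and 46-51% at d = 0.7. A baseline-adjusted analysis at d = 0.7 and r = 0.8 gives 87% (n = 15) and 91% (n = 17). The sample size is a separate matter, and the FERT point does not depend on it.

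**Method.** Power of a two-group t test from the noncentral t distribution, with 2n - 2 = 32 degrees of freedom and noncentrality d_eff × √(n/2) = d_eff × √8.5. The standardised effect d_eff depends on the analysis:

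- Visit 3 only: d_eff = d
- Change score: d_eff = d / √(2(1 - r))
- Baseline-adjusted (ANCOVA): d_eff = d / √(1 - r²)

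The one degree of freedom spent on the covariate is ignored.

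**Variance.** Relative to Visit 3 only, adjustment multiplies the variance of the group effect by 1 - r². At r = 0.3 this is 0.91, a 9% cut. At r = 0.8 it is 0.36, a 64% cut.

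**Worked ends of the range.** For d = 0.5, d_eff under adjustment is 0.5/√0.91 = 0.52 at r = 0.3 and 0.5/√0.36 = 0.83 at r = 0.8. For d = 0.7 the values are 0.73 and 1.17.

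**Power, 17 per group:**

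| d | r | 1 - r² | Visit 3 only | Change score | Baseline-adjusted |
|---|---|---|---|---|---|
| 0.5 | 0.3 | 0.91 | 29% | 22% | 32% |
| 0.5 | 0.5 | 0.75 | 29% | 29% | 37% |
| 0.5 | 0.7 | 0.51 | 29% | 45% | 51% |
| 0.5 | 0.8 | 0.36 | 29% | 61% | 65% |
| 0.7 | 0.3 | 0.91 | 51% | 39% | 55% |
| 0.7 | 0.5 | 0.75 | 51% | 51% | 63% |
| 0.7 | 0.7 | 0.51 | 51% | 72% | 79% |
| 0.7 | 0.8 | 0.36 | 51% | 88% | 91% |

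Adjustment is the best of the three in every row. The change score falls below Visit 3 only when r is under 0.5, equals it at r = 0.5, and approaches adjustment only when r is high.

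These figures describe a group comparison on a single FERT score. They do not give the power of the group × emotion interaction.

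**The case against.** **The text is only an outline.** Section 17 says so and promises a SAP, which may settle the visit, the score and the use of baseline. This has weight, since the FERT paragraph nowhere says that baseline is excluded. But the outline does more than stay silent: it removes FERT by heading from the model that uses both visits and names a different set of factors. That is a stated specification, and a SAP could carry it forward unchanged.

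**A Visit 3 analysis is valid.** Randomisation makes it unbiased, and its standard error already allows for chance baseline imbalance. This stands, so the cost is precision alone.

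**Baseline may be used after all.** A group × emotion ANOVA on change scores has exactly the factors named. This also stands. It would use baseline, though less efficiently than a covariate.

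**A reader might infer that both visits are pooled**, so that pre-drug scores dilute the drug effect. The Protocol does not support this. The paragraph names one within-subject factor, emotion, and nothing in it says that scores are averaged over visits.

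**A reader might also infer that FERT is necessarily analysed less precisely than the other tasks.** That is not established. The other tasks are left with a choice between ANCOVA and a mixed model, and a mixed model tested as group × time over two visits has the same limit as a change score.

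**FERT as a primary task is an inference.** Section 8.5 names no task, and section 8.3.5 announces three tasks but lists four. The inference from the battery list is reasonable, and FERT is described here only as part of that battery.

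**The gain may be small.** At r = 0.3 it is 3 to 4 percentage points of power. This is true, and r is unknown.

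**Conclusion.** The point holds as a loss of precision through the stated FERT model, not as a bias. Taken as written on Visit 3 data, the analysis discards a baseline that every participant provides. If r is between 0.3 and 0.8, using that baseline as a covariate cuts the variance of the group effect by about 9 to 64%. It raises power from 29% to 32-65% at d = 0.5 and from 51% to 55-91% at d = 0.7.

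These figures assume 17 per group, a two-sided 0.05 test, the stated effect size read as d, and a single FERT score. They show direction and range and are not a forecast. The size depends on r, but within this range adjustment does better than both Visit 3 only and change scores.

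**What to change.** Amend the FERT paragraph in section 17.1, or state in the SAP before it is approved and the data are locked, that:

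- the outcome is the Visit 3 FERT score for each emotion, with the score itself named;
- the model contains group, emotion and group × emotion;
- the same participant's Visit 2 score for that emotion enters as a covariate;
- participant is a random effect.

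The tests of interest are group and group × emotion. Adding a visit factor and testing group × visit is not an adequate substitute. With two visits it amounts to a change-score test, which at d = 0.7 and 17 per group gains nothing over Visit 3 only at r = 0.5 (51% in both) and loses power at r = 0.3 (39% against 51%).

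The cost is wording and, with one common slope for the covariate, about one degree of freedom. No new data are needed.

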#### **fMRI**

fMRI data will be preprocessed prior to analysis.

Resting state fMRI: (i) Network Analysis

The preprocessed cleaned functional data are temporally concatenated across subjects and decomposed into independent components using FSL MELODIC (Multivariate Exploratory Linear Optimized Decomposition into Independent Components). Dimensionality estimation for group maps will be set to a number of independent component maps and then identified as either being analogous to the most frequently reported major resting-state networks (RSNs) or reflecting noise (physiological, scanner, movement). Dual regression is then used to generate subject-specific versions of spatial maps and the associated time series from group-average spatial maps. Subsequently, we will test for statistically significant differences between the groups across all identified networks using FSL's randomize permutation testing tool. The RSNs of interest for this analysis are from the triple network model, comprising the  $\underline{DMN}$ , SN, and CEN. Other RSNs (i.e., visual, auditory) were analyzed as control regions where we did not expect to see changes with prucalopride. Statistics will be assessed using a familywise error—corrected cluster significance threshold of p < .05 applied to the suprathreshold clusters to correct for multiple comparisons at the voxel level. The general linear model will include the groups of interest for comparison: placebo > prucalopride and prucalopride > placebo.

Resting state fMRI: (ii) Seed Analysis

UOB ethics number: ERN 3117

For the seed analysis, predetermined region-specific masks are chosen based on the previous literature. Masks for these areas are binarized and thresholded before creating a standard- to high-resolution matrix, which is applied to each mask for each participant in turn to register the mask into each individual's functional (echoplanar imaging) space. We then extract the time series for each mask for each participant. First-level connectivity is calculated as the correlation (both positive and negative) of time series of the seed with all other voxels in the brain using FSL FEAT (https://fsl.fmrib.ox.ac.uk/fsl/fslwiki/FEAT). A white matter and cerebral spinal fluid (CSF) mask are also created in standard space and then registered into the individual's functional (echo-planar imaging) space before being included as covariates of no interest. We then use FSL FEAT to perform group-level analysis with 2 explanatory variables (prucalopride vs. placebo) testing for the contrasts placebo > prucalopride and prucalopride > placebo. Cluster-based thresholding (z > 3.1, familywise error p < 0.05) will be used to identify significant clusters for each seed analysis.

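### Both resting-state analyses test each map in two opposite directions at familywise p<0.05; if that level applies to each contrast, the false-positive chance per map is about 10%, not 5%

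*Protocol*

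**What the plan says.** Protocol section 17.1, fMRI, describes two resting-state analyses.

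- **Network analysis.** The plan says "we will test for statistically significant differences between the groups across all identified networks". The model has two contrasts, one in each direction: "for comparison: placebo > prucalopride and prucalopride > placebo". The threshold is given separately: "Statistics will be assessed using a familywise error—corrected cluster significance threshold of p < .05 applied to the suprathreshold clusters", and its purpose is "to correct for multiple comparisons at the voxel level". Three networks carry the hypothesis: "The RSNs of interest for this analysis are from the triple network model" (DMN, SN and CEN). Other networks serve as controls, and their number is not given.
- **Seed analysis.** The group model is again described as "testing for the contrasts placebo > prucalopride and prucalopride > placebo". The threshold is "Cluster-based thresholding (z > 3.1, familywise error p < 0.05) will be used to identify significant clusters for each seed analysis". The number of seeds is not given.

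Section 6 asks whether receptor activation has an effect compared with placebo, behavioural and/or neural, and names no direction. Section 8.5 makes task performance the primary outcome and functional connectivity a secondary one. Section 17 says that a SAP will be approved and uploaded before analysis.

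**The concern.** A familywise correction across voxels controls the chance of at least one false cluster in one statistic map. A directional contrast and its opposite are two statistic maps. If each is judged at 0.05 and a cluster in either would be reported as a group difference, the error rate of that report is close to twice the level printed in the plan.

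At stake is how much weight an imaging result can bear. Section 6 lets the research question be answered by neural effects, section 5.2 counts neuroimaging among the key outcome measures, and section 5.3 hopes for proof-of-principle evidence on neural effects to inform later trials. A reader of the results would take p<0.05 to mean a 5% chance of a false difference in a given network or seed map.

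**Working it through.** **Inputs**
- Directional contrasts per map: 2 (section 17.1, both analyses).
- Familywise level: 0.05 (section 17.1, both analyses).
- Networks of interest: 3 (section 17.1, network analysis).
- Whether 0.05 applies to each contrast or is shared by the pair: not stated, so both readings are worked.
- Dependence between directions and between networks: not stated, so independence and the upper bound are both shown.

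**Step 1. The plan's own figure.** The stated level is 0.05. For a difference in either direction it is recovered only if the two directions share it: 2 × 0.025 = 0.05 as an upper bound, or 1 − (1 − 0.025)² = 4.94% under independence.

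**Step 2. One map, 0.05 applied to each contrast**
- Independence: 1 − (1 − 0.05)² = 1 − 0.9025 = 9.75%.
- Upper bound under any dependence: 2 × 0.05 = 10%.

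**Step 3. Simulation check.** Null data were simulated with 18 per group and three smooth maps. A permutation test was run in both directions at 0.05 each, with 1,000 runs per setting. The voxel maximum stood in for the cluster statistic. The per-map error was 9.4%, 10.8% and 10.9% at between-map correlations of 0, 0.5 and 0.9. The values just above the 10% bound are simulation noise: counting each run once, the standard error is √(0.10 × 0.90 / 1000) = 0.95 percentage points.

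**Step 4. The three networks of interest, no correction across networks**

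| Rule per map | Independence | Upper bound |
|---|---|---|
| 0.05 in each direction | 1 − 0.95⁶ = 26.5% | 6 × 0.05 = 30% |
| 0.025 in each direction | 1 − 0.975⁶ = 14.1% | 6 × 0.025 = 15% |

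Under the first rule the simulation gave 25%, 27% and 20% at between-map correlations of 0, 0.5 and 0.9. If the three maps were fully dependent, the figure would fall to the per-map value of about 10%.

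So about half of the 26.5% (26.5 − 14.1 = 12.4 percentage points) comes from direction. The rest comes from testing three networks and would remain with correct two-sided tests.

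**The case against.** The strongest reply is that the Protocol never says 0.05 applies to each contrast. The network section gives one threshold in one sentence and lists the contrasts in another. The seed section ties the threshold to a seed analysis, which contains both contrasts. If 0.05 were shared, each map would stand at 5% and the point about direction would vanish. This stands as a qualification: the 9.75% is conditional. The per-contrast reading is still the natural one, because each contrast yields its own statistic map to be thresholded and no split of the level is mentioned.

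A second reply is that section 17.1 is only an outline and details belong to the SAP. That holds for correction across networks and for the number of seeds, whose absence here is no fault. It does not dispose of the direction point. The outline itself fixes the two contrasts and the level, and a SAP that carried them forward unchanged would inherit the problem.

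Third, the Protocol does not present 0.05 as the error rate of an overall imaging conclusion. That is correct. A reader might infer that the plan's true two-sided error is 26%, but the documents do not support this. The 26% is a familywise rate over six tests, it assumes independence, and only about half of it is due to direction. A reader might also add the seeds and reach a larger total, but the number of seeds is not given and any such total rests on a guess.

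Finally, imaging is secondary, and no rule says that one significant cluster settles the research question. This limits the consequence but does not restore the level.

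**Conclusion.** The point holds for each map. Testing both directions at familywise 0.05 gives a 9.75% chance of a false group difference under independence, and at most 10%, against a stated 5%. It applies to every network and every seed. It rests on two assumptions: that 0.05 is used for each contrast, and that a cluster in either direction would be reported as an effect. The second follows from the non-directional question in section 6.

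The primary behavioural comparison is not touched. A reader might infer that the plan must also correct jointly across networks and seeds. In a 36-person proof-of-concept study with imaging as a secondary outcome, that is a trade-off for the SAP to settle, and the Protocol's silence on it is not an error. Whatever is chosen, a finding in a single network should be read knowing that three uncorrected networks carry a familywise error of about 14% even after the fix below, or less if the maps are strongly correlated.

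**What to change.** In both the network and the seed analysis, state that each directional contrast is judged at familywise p<0.025, or replace the pair with one two-sided test at familywise p<0.05. Either choice holds each map to at most 5%. Record it in the SAP before it is approved and align the wording of section 17.1 with it.

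In the SAP, also say whether the three networks of interest and the seeds are corrected jointly. If not, report the number of maps tested beside any single-network or single-seed result.

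The cost is a sentence of text and a changed threshold in the same software, with no new data. The downside is that slightly fewer clusters will pass in a sample of 36.

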Study Design	Experimental medicine proof of concept study examining whether 5-HT 4 R agonism may affect cognition in healthy volunteers with psychotic-like experiences. 50% of the study population will be randomised to receive a highly-selective 5-HT 4 R agonist (prucalopride) and 50% will receive placebo for 7 days. Baseline and follow-up measures will include neurocognitive tasks and resting state fMRI; changes in mood, anxiety, subjective cognition, and blood biomarkers and prucalopride levels, will also be assessed
Primary Objectives	To determine if pharmacologically activating the 5-HT 4 R compared to placebo has an effect on acute neurocognition in healthy volunteers with psychotic-like experiences
Study Endpoints	Data will be collected at the end of 7-10 days' prucalopride or placebo for each participant
Study Duration	2 years

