# 8.3.6 3T MRI / MRS scan (up to 40 minutes including preparation time) — BASELINE AND FOLLOW-UP **T1** (5 min) — ONCE ONLY

A Magnetization Prepared Rapid Acquisition Gradient Echo (MPRAGE) with high spatial resolution (1mm or better) that provides an excellent contrast between grey and white matter. This measure is required for anatomical segmentation of the brain.

#### Resting-state functional MRI (10 min) - BOTH VISITS 2 AND 3

A multi-band gradient echo acquisition sensitive to blood oxygen levels (BOLD) most robustly in grey matter. This measure provides an estimate of functional connectivity within and between particular brain networks. Participants will be asked to have eyes closed and eyes open at specific points of the scan for consistency. After the visit, participants will be asked to verbally recall what they were thinking during the scan (warning of this question will be given).

#### Magnetic resonance spectroscopy (MRS) (10 minutes) – BOTH VISITS 2 AND 3

sLASER MRS to focus on the hippocampus (initial scoping to ensure practical already completed). Magnetic resonance spectroscopy (MRS) is a non-invasive neuroimaging technique that measures the chemical composition and metabolism of tissues, most commonly used to assess brain metabolites such as choline and glutamate / glutamine. MRS does not represent any additional risks to participants compared to MRI.

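### Resting-state fMRI is acquired before and on drug, but the group models name only the two arms, so on the natural reading the drug effect is tested without the baseline scan and loses precision

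*Protocol*

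**What the plan says.** **Acquisition.** The synopsis states: "Baseline and follow-up measures will include neurocognitive tasks and resting state fMRI". Section 8.3.6 gives the schedule as "Resting-state functional MRI (10 min) - BOTH VISITS 2 AND 3", whereas the structural scan is taken once only. Section 8.5 lists functional connectivity as a secondary outcome, and Section 5.2 counts neuroimaging among the key outcome measures.

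**Network analysis (Section 17.1, fMRI, part i).** The input is described as follows: "The preprocessed cleaned functional data are temporally concatenated across subjects". After dual regression, the group test is: "The general linear model will include the groups of interest for comparison: placebo > prucalopride and prucalopride > placebo".

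**Seed analysis (Section 17.1, fMRI, part ii).** The input is again described per person: "We then extract the time series for each mask for each participant". White-matter and CSF masks are registered to the individual's functional space "before being included as covariates of no interest". The team will then "perform group-level analysis with 2 explanatory variables (prucalopride vs. placebo) testing for the contrasts placebo > prucalopride and prucalopride > placebo".

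**Other analyses in Section 17.1.** The questionnaire analyses, and the behavioural analyses other than the FERT, compare the arms over baseline and follow-up, using ANOVA or ANCOVA or linear mixed models.

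**The concern.** The design obtains a pre-drug connectivity map for every participant, but the group models as written have no term that uses it. The seed model is fixed at two explanatory variables, one per arm. The network model names only the arms. The only covariates mentioned are nuisance signals in the individual-level step.

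If the test uses Visit 3 alone, stable differences between people stay in the error term and a chance difference between the arms at baseline is not adjusted for. With at most 18 per arm, both matter. Section 5.3 gives an effect-size estimate for later trials as one purpose of the study, so precision is part of its value. Section 12 itself recognises baseline differences in cognition and mood as a threat to detecting signal, but its mitigation covers only baseline mood and subjective cognition.

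**Working it through.** **The plan's own figure.** The protocol gives no precision or power figure for fMRI. Section 16.1 (15-17 per group, 85-90% power, effect size 0.5-0.7, alpha 0.05) refers to behavioural measures. A two-sided two-sample t test with those inputs gives power of 0.26 (n = 15, d = 0.5) to 0.51 (n = 17, d = 0.7), so the stated range is not reproduced. That is a separate matter, and nothing below depends on it.

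**Inputs.** There are 18 per arm, 36 in total (Section 16.1). The correlation r between the Visit 2 and Visit 3 measures is not in the protocol and is assumed to be 0.3 to 0.6. The formulas are for one standardised endpoint with equal variance at the two visits.

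**Step 1: size of chance baseline imbalance.** The SD of the between-arm baseline difference is sqrt(2/18) = 0.33 SD. It exceeds 0.5 SD in either direction with probability of about 13%. On average r times the imbalance carries into a Visit 3-only contrast: 0.3 × 0.33 = 0.10 SD to 0.6 × 0.33 = 0.20 SD for a typical imbalance.

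**Step 2: variance of the drug effect relative to Visit 3 alone (= 1).** The baseline covariate gives 1 − r². The difference map gives 2(1 − r).

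| r (assumed) | Covariate, 1 − r² | Equivalent N, 36/(1 − r²) | Difference, 2(1 − r) |
|---|---|---|---|
| 0.3 | 0.91 | 39.6 | 1.40 |
| 0.5 | 0.75 | 48.0 | 1.00 |
| 0.6 | 0.64 | 56.3 | 0.80 |

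The covariate lowers the variance by 9 to 36%. A difference map is noisier than Visit 3 alone when r is below 0.5, and less noisy only when r is above 0.5.

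**Step 3: cost of estimating the covariate.** The variance is inflated by about 1 + 1/(N − 4) = 1 + 1/32 = 1.03. The ratios become 0.91 × 1.03 = 0.94, 0.75 × 1.03 = 0.77 and 0.64 × 1.03 = 0.66.

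**Step 4: cost of lost participants.** Suppose two of the 36 lack a usable Visit 2 scan (an assumption). Multiplying by 36/34 gives 0.94 × 1.06 = 0.99 at r = 0.3, 0.82 at r = 0.5 and 0.70 at r = 0.6. The gain almost vanishes at the low end of the range and remains worthwhile from r = 0.5.

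**Step 5: illustrative power.** For one endpoint with d = 0.7, 17 per arm, two-sided 0.05 (noncentral t), the two-group model on Visit 3 has power 0.51. With the covariate, power is 0.55, 0.63 and 0.70 at r = 0.3, 0.5 and 0.6. Voxelwise, cluster-thresholded inference will give different values.

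**The case against.** **The wording does not strictly exclude the baseline.** A two-group model on one Visit 3 minus Visit 2 map per participant also has exactly two explanatory variables and the two stated contrasts. A reader might infer that the plan definitely discards the baseline scan, but the protocol never says which map enters the group model. This part of the objection stands. However, no subtraction step is described, and one time series per mask per participant points to a single scan per person. Even if difference maps were meant, the text would have to say so.

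**The two models are not equally explicit.** Only the seed analysis fixes the number of explanatory variables. The network text says what the model will include, which leaves room for other terms. This stands too.

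**Two scans as independent.** A reader might infer that both scans could be entered as separate observations, breaking exchangeability in the permutation test. Nothing supports that: the text speaks of subjects and participants throughout.

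**A Visit 3-only contrast is valid.** Allocation is randomised and blinded, so the contrast is unbiased, and chance imbalance is already in its standard error. A reader might infer bias or an inflated false-positive rate, and neither follows. The loss is precision and adjustment for the imbalance that happens to occur.

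**This belongs in the SAP.** Section 17 calls its text an outline, and the SAP is not at hand. But the outline fixes the seed design matrix, contrasts and cluster threshold, and it names both time points for the questionnaires and most behavioural tasks. The point concerns a model as stated, not a detail left for later.

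**The size rests on an assumed correlation.** It does, and at r = 0.3 the gain is small (Steps 3 and 4).

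**Conclusion.** The point holds as one of efficiency and clarity. The seed model is specified by arm only, the network model names only the arms, and neither uses the pre-drug scan in any stated way. On the natural one-scan-per-participant reading, the test is a valid, unbiased Visit 3 comparison that leaves a collected baseline unused. Using it would lower the variance of a single endpoint by about 9 to 36% for an assumed scan-rescan correlation of 0.3 to 0.6, or about 6 to 34% after the cost of estimating the covariate, and would adjust for a chance imbalance with SD 0.33 SD. These figures assume 18 per arm with complete scans and equal variances at the two visits; voxelwise gains will differ. The documents do not support a claim of bias, of pseudoreplication, or of a definite decision to discard the baseline. Connectivity is a secondary outcome, so the weight is moderate. The change is worth making because it costs almost nothing if settled before analysis.

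**What to change.** In both the network and the seed parts of Section 17.1, state that the Visit 3 map is compared between arms with the participant's own Visit 2 map as a voxelwise covariate, and that one map per person enters the group test. This also holds if scans from both visits are used in the group decomposition.

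A Visit 3 minus Visit 2 map per participant is an acceptable alternative. It fits the two-variable seed design as written, but it is more precise than Visit 3 alone only if the correlation exceeds 0.5. Whichever form is chosen should be named before the data are locked, so that the choice is not made after seeing the results.

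The cost is a change of wording and a little more processing. No new scans are needed. The downside is that participants without a usable Visit 2 scan drop out of that model.
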